APPENDIX B

Subject Home Instruction Sheet

Clinical Evaluation of the Tolerability of Using a Post Treatment Topical Adjuvant Combination Following Fractional Radiofrequency Ablation Using the Venus Viva™ - Protocol CS0116

- Tiny scabs about the size of a small pinprick will usually form 24-72 hours post-treatment. The scabs should not be scratched and should be allowed to shed off naturally, usually 1-2 days after their formation. In case of discomfort, cool/cold compress (but not ice packs) may be applied.
- On the day after the treatment, activities where potential damage due to overheating, direct rubbing or other contact may occur (e.g., Jacuzzi, kickboxing, massage) should be avoided.
- No moisturizer or other topicals should be applied after the treatment. Make-up may be applied only 24 hours after each treatment, unless an adverse event occurs in the area.
- You may use regular soaps, but not scrub soaps or exfoliants to clean the treatment area.
- Tanning of any sort is not allowed of the treated areas. Use a high factor sunscreen with SPF of at least 30 and to protect the treated area from direct sunlight for the entire period of the study.
- A follow-up telephone call will be made to you 24 and 72 hours after the first treatment and 24 hours after the second treatment to see how you are doing and to remind you to complete and return the Subject Tolerability Scale at your next visit.

Site contact information.

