8. RANDOMIZATION

Subjects will be randomized to receive either standard of care (SOC) treatment (no topical therapy for 24 hours post fractional RF treatment) or a topical adjuvant combination treatment utilizing SCR Complex™ and Bio Cel™. The order of treatment will be assigned to subjects through subject number. All subjects will resume skin care as per VenusSkin protocol 24 hours post fractional RF treatments.

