- The immediate responses, indicative of the desired effect, are erythema and edema in the immediate area of the stamp and possibly also around it. The edema usually appears 1-2 minutes post-treatment and reaches its peak (of up to moderate edema) within 30 minutes. It should be noted that erythema is not easily noticeable, if at all, in darker skin types, so the edema will indicate a more significant effect in these subjects.
- Treatment consists of a single pass over the designated area.
- Unless otherwise instructed, the energy parameters can be modified between the treatment visits, as per the Investigator's discretion.
- It is recommended that throughout the study, that one staff member administer the treatments and another staff member perform the evaluations of the treatment area.

Post Fractional RF Treatment

- Subject Discomfort Assessment recorded on a 100mm visual analogue scale (VAS) immediately post treatment.
- Subject Tolerability Scale immediately post treatment.
- Subjects will receive either the adjuvant combination treatment (SCR Complex™ followed by Bio Cel™ occlusive gel applied to the treatment area) or SOC (no topical applications to treatment for 24 hours post fractional RF treatment).
- Subjects will be asked to complete the Subject Home Tolerability Scale at 24 hours and 72 hours post-treatment
- Subjects will be provided with the Subject Home Instruction Sheet (Appendix B).
- A follow-up telephone call will be made to the subject 24 and 72 hours after the first treatment and 24 hours after the second treatment. Study staff will ask the subject to report on the treatment using the Self-Report Adverse Event Questionnaire (Appendix C) and remind the subject to complete and return to the clinic with their completed Subject Home Tolerability Scale at each visit.

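### The home instruction sheet (Appendix B) bans topicals with no end time and prescribes sunscreen with no start time, so subjects can read it in ways that break the 24-hour rules of Sections 8 and 11.2

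*Combined protocol and SAP*

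**What the plan says.** **Protocol rules.** Section 8 (Randomization) defines the comparator as "standard of care (SOC) treatment (no topical therapy for 24 hours post fractional RF treatment". Section 11.2 (Treatment Visits) repeats it: "no topical applications to treatment for 24 hours post fractional RF treatment". For both arms, Section 8 adds: "All subjects will resume skin care as per VenusSkin protocol 24 hours post fractional RF treatments". The VenusSkin protocol is not in the documents.

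**What the subject is told.** Section 11.2 states "Subjects will be provided with the Subject Home Instruction Sheet (Appendix B") and describes no arm-specific version. On topicals the sheet says "No moisturizer or other topicals should be applied after the treatment". The next sentence of the same bullet says "Make-up may be applied only 24 hours after each treatment, unless an adverse event occurs in the area". A later bullet says "Use a high factor sunscreen with SPF of at least 30 and to protect the treated area from direct sunlight for the entire period"; the period meant is that of the whole trial.

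**Outcome and contacts.** Section 14 summarises tolerability immediately, at 24 hours and at 72 hours after treatment; this is the primary outcome. Under Section 11.2 a telephone "call will be made to the subject 24 and 72 hours after the first treatment and 24 hours after the second treatment". The stated purposes of the call are the Appendix C questionnaire and a reminder to complete the tolerability scale.

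**The concern.** The SOC arm has no study product. It is defined by abstention from topicals for 24 hours, and most of that time is spent at home. What the subject is told in writing is therefore part of how the comparator is delivered. The sheet does not state the 24-hour rule for topicals. It states a ban that never ends and a sunscreen instruction that does not exclude the day of treatment.

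Two things are at stake. One is adherence to the assigned no-topical period before the 24 h tolerability reading. The other is adherence to the common skin care before the 72 h reading.

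**Working it through.** No arithmetic figure is at issue. The check sets the timing rules side by side and follows what different readers of the sheet would do.

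**Rules by time window**

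| Window after treatment | Sections 8 and 11.2 | Appendix B ban | Appendix B sunscreen line |
|---|---|---|---|
| 0 to 24 h | SOC: no topical. Adjuvant arm: SCR Complex, then Bio Cel; no stated ban on other topicals | No topicals | Use SPF 30+; no exception for this window |
| After 24 h | Both arms resume VenusSkin care | No topicals; no end stated | Use SPF 30+ |

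Read literally, the last two columns disagree in both windows. In the first, the sunscreen line departs from the SOC definition. In the second, the ban departs from the resumption of skin care, provided that VenusSkin care includes at least one product applied to the skin.

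**What a subject might do**

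1. Takes the ban as lasting 24 hours, counts sunscreen as a topical, and starts sunscreen afterwards. No rule in Section 8 or 11.2 is broken.
2. Takes the ban as lasting 24 hours but applies sunscreen on the day of treatment. In SOC this breaks the arm definition before the 24 h reading. In the adjuvant arm it breaks no rule in Sections 8 or 11.2.
3. Takes the ban as open-ended and as covering sunscreen. The SOC definition is kept. In either arm, planned skin care is omitted before the 72 h reading if VenusSkin care includes a topical.
4. Exempts sunscreen but reads the ban as open-ended for everything else. An SOC subject who applies sunscreen on the day then has both departures, the second under the same VenusSkin assumption.

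The documents give no basis for saying how many subjects fall into each group.

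**Which readings are exposed.** There are 3 times x 2 treatments = 6 scheduled tolerability readings per subject. The 2 immediate readings are taken before the subject applies or withholds anything at home after that treatment. The other 6 - 2 = 4, at 24 h and 72 h, come after home use begins. These 4 are where exposure is possible; they are not a count of compromised readings, which for reader 1 is zero.

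**Whether use would be recorded.** Appendix C asks about health, the treatment area and medications. Concomitant medications are also reviewed at treatment visits and at follow-up (Sections 11.2 and 11.3). These could pick up some topical use, but a subject may not think of sunscreen or moisturizer as a medication. Section 15 has deviations noted in source documents, but a subject who follows the sheet has no reason to report one. The CRF is not included, so other capture is possible.

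**The case against.** The strongest reply is that the intended rule is easy to see. The make-up sentence in the same bullet gives 24 hours, and Section 8 gives 24 hours for resuming skin care. A sensible subject would treat the ban as the specific post-treatment rule and sunscreen as the general one. The sunscreen sentence is also garbled, and its whole-study period may attach only to avoiding sunlight. Staff telephone every subject 24 hours after each treatment, just when skin care resumes.

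Much of this stands. A 24-hour limit was probably intended, and a subject can comply with no breach. It does not remove the point. The 24 hours on the sheet is attached to make-up only. If the study period applies only to sun avoidance, sunscreen has no timing at all. The call has no stated step on skin care, and at 24 hours it comes too late to prevent sunscreen use in the SOC window.

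A reader might infer that a fixed number of hours or readings per subject is compromised. The documents do not support that, because the number depends on the subject's reading and can be zero. A reader might also infer bias towards one arm. Both arms get the same sheet, and nothing in the documents shows a direction or any effect on scores.

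**Conclusion.** The point holds as a contradiction in the subject-facing instructions. Appendix B's two lines are inconsistent with each other. Depending on the reading, they can also be inconsistent with the SOC definition in Sections 8 and 11.2 and with the resumption of skin care in Section 8.

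The conflict with the SOC definition arises only if an SOC subject applies sunscreen in the first 24 hours. The conflict with resumed skin care rests on two assumptions: that the subject reads the ban literally, and that VenusSkin care includes a topical. If it includes none, that second conflict disappears.

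Exposure runs from none upward and cannot be sized. The 24 h and 72 h tolerability readings are the ones exposed. The change is worth making because the sheet bears on delivery of the comparator, and correcting it is cheap.

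**What to change.** Reword Appendix B along these lines: *For 24 hours after each treatment, apply no moisturizer, sunscreen or other topicals except any study product assigned to you; keep the area out of direct sun. From 24 hours, resume skin care as instructed by the site (VenusSkin protocol) and use SPF 30+ sunscreen.*

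The sponsor should settle two points before the text is fixed:

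- **Whether study product is applied only at the clinic.** Section 11.2 lists application among the post-treatment steps, while the Synopsis describes SCR Complex as indicated into the first days of healing.
- **Whether the 24-hour sunscreen restriction should apply in the adjuvant arm.** Sections 8 and 11.2 impose the no-topical rule on SOC only. Withholding sunscreen after an ablative procedure also needs clinical input.

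Optionally, add one question to Appendix C on which products have been applied to the face since treatment and when, because the existing medication question may miss cosmetics. Appendix C is already used at 4 contacts (3 calls + 1 follow-up visit), so no visit or call is added.

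The cost is ethics approval of a revised one-page sheet, plus one line on an existing form if the question is added.

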APPENDIX C

Self-Report Adverse Event Questionnaire

Date:	___ / ___ / _____ <small>DD MMM YYYY</small>	Patient Code:	___ / ___ / _____ <small>Site # Pt. Initials Pt. #</small>
Have there been any changes in your health since your last visit?			Yes / No
If Yes, please describe the event in detail:			
Have there been any changes in your treatment area since your last visit?			Yes / No
If Yes, please describe the event in detail:			
Have there been any changes in your medications?			Yes / No
If Yes, please specify:			
Remind subject to complete the Subject Home Tolerability Scale.			Yes / No

Evaluator Name / Signature

DD-MMM-YYYY

APPENDIX D

Global Aesthetic Improvement (GAI) Scale

Score		
(3)	Very Much Improved	Optimal cosmetic result.
(2)	Much Improved	Marked improvement in appearance from the initial condition, but not completely optimal.
(1)	Improved	Obvious improvement in appearance from the initial condition.
(0)	No Change	Appearance is essentially the same as baseline.
(-1)	Worse	Appearance is worse than the original condition
(-2)	Much Worse	Marked worsening in appearance from the initial condition.
(-3)	Very Much Worse	Obvious worsening in appearance from the initial condition.
